6.3 Secondary outcomes analysis

Our approach to analysis of secondary outcomes will mirror the approach outlined above for primary outcome analysis.

The secondary outcomes are:

- Ability to understand and/or experience the emotions of others (empathy), as measured by the Basic Empathy Scale (BES) (Jolliffe and Farrington, 2006) at baseline and T2 (five months post-randomisation).
- Pro-social values and behaviours measured by the Strengths and Difficulties Questionnaire pro-social behaviour subscale (SDQ) (Goodman, 2005) at baseline and T2 (five months post-randomisation).
- Behavioural difficulties, measured by the Strength and Difficulties Questionnaire externalising behaviours scale (SDQ) (Goodman, 2005) at baseline and T2 (five months post-randomisation).

For each secondary outcome we will conduct analyses of impact on the measures outlined above. This will be conducted using the same ANCOVA model specified for the primary outcomes measure outlined in Section 6.2 Primary outcome analysis above, which will include the baseline measurement for the respective secondary outcome variable where relevant.

We will also run robustness checks to assess the underlying assumptions for ANCOVA for each secondary outcome measure. This will include assessing normality of the data using histograms and K-S tests. If the data does not meet these assumptions, we will run a non-parametric ANCOVA analysis. This will be determined once all data has been collected.

These analyses will be conducted in SPSS 25.¹¹

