6.8 Missing data

Throughout the trial, the evaluation team will work closely with the Cerridwen intervention team to support the collection of high quality and complete data for all young people. However, missing data may arise due to either item non-completion or sample attrition (i.e. young people who do not complete all items of the baseline or the T2 questionnaires). We will assess both the extent of missingness and patterns of missingness in the data. In line with YEF guidance (2021a) we will report on both: (1) the proportion of missing data in the trial, and (2) the extent and pattern of missingness in the data. This will involve analysis of whether data is missing completely at random (MCAR), missing at random (MAR), or missing not at random (MNAR). MCAR and MAR mean that complete cases are unlikely to be biased subsequent to adjustment but may be underpowered, while MNAR suggests that structural bias has been introduced to the sample.

We will attempt to establish the missing mechanism (i.e. which variables in the data are predictive of non-response) through logistic regression models. This will model the presence of missing outcomes data with additional information that may be predictive of missingness. We will conduct this analysis in line with the flow chart in Figure 1 in the YEF analysis guidance (2021a). This outlines the following approach:

- If the prevalence of missing data is less than 5%, no further action is required as complete case analysis is unlikely to be biased.
- If outcomes data is MAR conditional on co-variates, we will include these co-variates in our primary analysis model and discuss the implications in full.
- If a covariate is MAR conditional on other covariates, we will conduct multiple imputation (MI). Treatment effects from the MI analysis will be reported in addition to estimates from the model outlined in Section 6.2 Primary outcome analysis. Any differences between the two and their implications will be discussed in full.

• If missing data cannot be fully explained by the other variables in the dataset, data is likely to be MNAR. In this scenario we will conduct a sensitivity analysis alongside the primary impact analyses.

We will only conduct the above analyses for the primary outcome analysis, as all secondary outcomes analysis, subgroup analysis and further analysis is tentative and exploratory in nature.

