6.11 Presentation of outcomes

Effect sizes will be calculated using Hedges' g, as specified in the following equation:

$$ES = \frac{(\bar{Y}_T - \bar{Y}_C)_{adjusted}}{sd_{pooled}}$$

Where:

• $(\bar{Y}_T - \bar{Y}_C)_{adjusted}$ is the ANCOVA difference in means between the treatment and control groups adjusted for baseline outcomes measures and area, as specified in the primary outcomes model.

 sd_{pooled} is the unconditional pooled standard deviation of the two groups. 12

With a sample of greater than 20 there is limited difference with Cohen's d. However, if the standard deviations between the treatment and control group are different, we would propose to use Glass' delta, which only uses the control group's standard deviation (Lipsey & Wilson, 2001).

We will report the statistical uncertainty associated with the effect sizes using both 95% confidence intervals (CIs) and two-tailed p-values, with statistical significance assessed at the conventional threshold of p < 0.05. Confidence intervals will be calculated using the following formula:

$$g \pm \Phi^{-1} \left(1 - \frac{\alpha}{2}\right) g_{se}$$

Where:

• Φ^{-1} is the percent point function of the normal distribution.

• g_{se} the standard error of the g statistic (noted as ES above).

All estimations and their statistical uncertainty will be reported, and the implications of both the point estimates and confidence intervals will be set out. In addition, all reporting will consider findings in light of the existing evidence base. This will be triangulated with the evidence collected from the implementation and process evaluation on the quality and context of delivery, the existence of theoretical causal mechanisms, and the experiences and

 $^{^{12}}$ $sd_{pooled}=\sqrt{rac{(n_1-1)sd_1^2+(n_2-1)sd_2^2}{n_1+n_2-2}}$, where n_1 and n_2 are the sample size for groups 1 and 2 respectively, and sd_1 and sd_2 are the standard deviations of group 1 and group 2 respectively.

perspectives of young people, parents and carers, key staff members, and wider stakeholders who participate in semi-structured interviews.

7 References

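### Section 6.8 limits missing-data assessment and adjustment to the SRDS, so the secondary outcomes are estimated from complete cases although planned attrition exceeds the SAP's own 5% threshold

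*SAP*

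**What the plan says.** SAP section 6.8 plans logistic models of missingness followed by steps that depend on what they show:

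- Low missingness: "If the prevalence of missing data is less than 5%, no further action is required".
- Outcome missing at random: "If outcomes data is MAR conditional on co-variates, we will include these co-variates in our primary analysis model".
- Covariate missing at random: multiple imputation, reported beside the main estimate.
- Suspected missing not at random: a sensitivity analysis, not further described.

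The section then restricts all of this: "We will only conduct the above analyses for the primary outcome analysis". The reason given is that "all secondary outcomes analysis, subgroup analysis and further analysis is tentative and exploratory in nature".

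Section 6.3 introduces the secondary outcomes differently: "Our approach to analysis of secondary outcomes will mirror the approach outlined above for primary outcome analysis". The model is the same ANCOVA, "which will include the baseline measurement for the respective secondary outcome variable where relevant". The section does not describe these outcomes as exploratory. Section 6.11 states "We will report the statistical uncertainty associated with the effect sizes using both 95% confidence intervals (CIs) and two-tailed p-values". It sets the significance level at 0.05 and makes no exception for secondary outcomes.

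**The concern.** Section 4.3 says every scale is collected by survey or paper questionnaire at baseline and at five months. A young person lost at five months is therefore lost for every outcome, and attrition affects the secondary scores much as it affects the SRDS.

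The primary model contains baseline SRDS, so dropout that depends on baseline offending is already allowed for there. Each secondary model contains only its own baseline score and area. If young people who offend more at baseline leave at different rates in the two arms, the secondary models do not correct for it, and the one step that could add baseline SRDS is reserved for the primary outcome.

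At stake are the estimates for empathy, prosocial behaviour and externalising behaviour. They will be presented with the same inferential apparatus as the primary result. Calling an estimate exploratory lowers the claim made for it but does not change its bias.

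**Working it through.** **1. The SAP's own figures.** Inputs from section 5.1: MDES 0.20, baseline/follow-up correlation 0.5, two-sided alpha 0.05, power 80%.

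- n per arm = 2 × (1.96 + 0.84)² × (1 − 0.5²) / 0.20² ≈ 294.3, rounded up to 295. The total is 590 against the stated 592, so the figure reproduces.
- At the updated analysis sample of 367, the same approach gives an MDES of 0.254 against the stated 0.25.
- The standard error of a standardised effect at 367 is √(4 × 0.75 / 367) ≈ 0.09.

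**2. Is the 5% threshold expected to be passed?** The table in section 5.1 uses attrition of 10%, 12% and 21%. All exceed 5%, so the steps in 6.8 would be expected to apply. Section 6.6 sets 31% as the level for a formal assessment of power and bias.

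**3. When is the complete-case ANCOVA biased?** This was checked by simulation with 2,000,000 records per scenario, a true effect of 0.2 SD, a coefficient of 0.5 on the outcome's own baseline, and area omitted. The SAP does not give the following assumptions: an extra baseline predictor with coefficient 0.3 on the outcome, and a dropout log-odds slope of 0.7 in size. Bias is in SD units.

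| What dropout depends on | Attrition 10% / 12% / 21% / 31% | After adding the extra predictor |
|---|---|---|
| Own baseline, opposite directions by arm | 0.00 throughout | 0.00 |
| Extra predictor, same in both arms | 0.00 throughout | 0.00 |
| Extra predictor, opposite directions by arm | −0.04 / −0.05 / −0.08 / −0.12 | 0.00 |
| The outcome itself, opposite directions by arm (not at random) | −0.10 / −0.12 / −0.21 / −0.31 | −0.09 / −0.11 / −0.18 / −0.27 |

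The adjustment in 6.8 makes a decisive difference only in the third row. Fully opposite slopes are a severe assumption.

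**4. Less extreme slopes, with baseline SRDS as the extra predictor, 20% attrition.** These are again assumptions.

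- Equal slopes of 0.8 in both arms: bias about 0.
- Slopes 0.6 (control) and 0.3 (treatment): about 0.01 SD.
- Slopes 0.8 to 1.0 (control) and −0.2 to 0.2 (treatment), SRDS coefficient −0.2 to −0.3 after own baseline: about 0.02 to 0.065 SD.
- Steepest of these slopes, but SRDS coefficient only −0.1 and correlation −0.4 between the two baselines: about 0.015 to 0.02 SD.
- At 12% attrition, the third case falls to about 0.01 to 0.04 SD.
- With baseline SRDS in the model, the bias is within about 0.004 SD.

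**5. Scale.** The top of this range is 0.065 / 0.25 = 26% of the MDES at 367, and 0.065 / 0.09 ≈ 0.7 standard errors.

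**The case against.** The restriction is a disclosed scope decision with its reason in the same sentence. The mirroring in 6.3 can fairly be read as referring to the ANCOVA in 6.2, with missing data left to 6.8. Confidence intervals and p-values are compatible with exploratory status. This stands to the extent that the SAP has made a choice and not an oversight. It leaves 6.3 and 6.11 without the label on which 6.8 relies.

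A reader might infer that the secondary outcomes have no protection at all. The SAP does not support that. Section 6.6 tracks overall and differential attrition and mentions sensitivity analysis or imputation without limiting them to the primary outcome. Section 6.7 plans a table of five-month completers that includes all the scales. The item-level imputation considered at the end of 6.8 is not expressly limited to the SRDS. These provisions could reveal a problem, but none commits to adjusting a secondary estimate for dropout.

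A reader might also infer that the secondary estimates will be biased and that the planned method would cure this. Neither follows. Bias is absent in two of the four tabulated scenarios. Where data are missing not at random, most of it remains after the planned step. The SAP contains no dropout slope and no coefficient linking SRDS to the other scales, so every size quoted is assumed.

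**Conclusion.** The point holds as a correctable analysis choice of modest weight. Section 6.8 withholds its own missing-data steps from outcomes that 6.3 and 6.11 treat like the primary, under planned attrition of two to four times the 5% threshold (10/5 = 2; 21/5 ≈ 4). The resulting complete-case estimates would be biased if a measured variable outside the model both predicts the outcome and drives dropout differently by arm. A contrast between weekly mentoring and light-touch support makes different dropout patterns possible, but the SAP has no evidence that they occur.

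The size cannot be derived from the SAP. Under the assumptions in step 4 it is about 0 to 0.065 SD at 20% attrition. The fully opposite slopes of step 3 give 0.08 SD at 21%. Adjustment removes the bias only under missingness at random given measured covariates.

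**What to change.** In section 6.8, delete the restriction for the secondary outcomes and apply the same steps to the BES, SDQ prosocial and SDQ externalising scores:

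- fit the missingness model for each;
- add to each secondary ANCOVA the measured baseline variables found to predict dropout, including baseline SRDS;
- use multiple imputation where a covariate is missing;
- run a sensitivity analysis if missingness not at random is suspected.

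Joint imputation of all outcomes is not needed. The SAP does not plan it even for the primary outcome, and in the simulations baseline SRDS as a covariate was enough when data were missing at random.

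If the secondary outcomes are meant to be exploratory, say so in 6.3 and 6.11. The cost is a little more analysis work. All the variables are already being collected.

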6.9 Compliance

As outlined in Section 6.1 Overview all analyses will be conducted on an intent-to-treat basis. This means that overall compliance for the purposes of the efficacy study will be met when young people have been randomised and allocated into the treatment or control group.

However, we acknowledge that intent-to-treat analysis may underestimate the efficacy of the intervention if some young people in either trial arm do not adhere to their assigned treatment. To examine this, we will conduct Complier Average Causal Effect (CACE) analysis, which will indicate treatment effects amongst those who comply with the intervention. However, any analysis of treatment effects in the presence of non-compliance will also be exploratory. This will be estimated using two-stage least squares (2SLS) regression (Gerber and Green, 2012), which uses the following two stages:

- 1. The first stage will model the compliance variable (i.e. number of sessions) using the same explanatory variables used for the primary analysis. This will be a logistic regression model used to generate predicted compliance.
- 2. The second stage models will use predicted compliance in place of the allocation group variable in the ITT primary analysis specified in Section 6.2 Primary outcome analysis to generate the CACE estimates.

We will report the results from the first stage of the 2SLS, along with the correlation between the instrument and endogenous variable and the associated F-test. Interpretations of the CACE estimates will be provided in the final report.

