Those recruited and randomly allocated to the treatment group receive weekly, two to three-hour one-to-one case management/mentoring sessions over a six-month period. Those randomly allocated to the control group receive light-touch, structured signposting and safeguarding support, provided by MAC. For more detail on the participant journey, please see the trial protocol.

Figure 1 below presents an overview of the trial design.

Figure 1: Trial design overview

Trial design, including number of arms		Two-arm parallel randomised control trial with random allocation at the young person level	
Unit of randomisation		Individual young person	
Stratification variables (if applicable)		None	
variable		Self-reported offending (violent or non-violent or general)	

³ Examples of organisations include: Atal Y Fro, Action for Children, Amber Project, Barnardo's, Fearless, Llamau, Platform, St Giles, The Hangout and Women's Aid.

⁴ Self-referrals may form a small proportion of overall referrals. Self-referrals will be subject to the same assessment of eligibility as other referrals. Eligibility and consent are re-confirmed in the first meeting with the young person to ensure only the intended cohort access Cerridwen.

⁵ See: https://www.sealedenvelope.com/. last accessed 10 January 2025.

Primary outcome	measure (instrument, scale, source)	Self-Reported Delinquency Scale (volume score)	
	variable(s)	Empathy Pro-social values and behaviours Behavioural difficulties	
Secondary outcome(s)	measure(s) (instrument, scale, source)	Empathy, measured by the Basic Empathy Scale (Jolliffe and Farrington, 2006). Pro-social values and behaviours, measured by the Strengths and Difficulties Questionnaire pro-social behaviour subscale (SDQ) (Goodman, 2005). Behavioural difficulties, measured by the Strength and Difficulties Questionnaire externalising behaviours scale (combining conduct problems and hyperactivity/inattention subscales) (SDQ) (Goodman, 2005).	
Baseline for	variable	Self-reported offending (violent and non-violent or general)	
primary outcome	measure (instrument, scale, source)	Self-Reported Delinquency Scale (volume score)	
	variable	Empathy Pro-social values and behaviours Behavioural difficulties	

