- Y_i is the T2 (five months post-randomisation) volume score for self-reported delinquency as measured by the SRDS.
- Baseline_i is the baseline outcome measure of the SRDS volume score for young person
 i.
- $Group_i$ is a dummy variable for allocation group, i.e. 1 for the treatment group and 0 for the control group.
- β_2 is the average treatment effect, i.e. the primary parameter of interest for the trial.
- $Area_k$ is a vector of K-1 binary area dummy variables.
- ε_i is the error/residual.
- σ^2 is the variance.

Specifying this model upfront will help to ensure that the analyses avoid the "fishing problem" and the "curse of dimensionality" (Humphreys et al 2013; Hayes, 2011).

We will also run robustness checks to assess the underlying assumptions for ANCOVA (e.g., linearity, homogeneity of regression slopes, normality of residuals, homoscedasticity) before conducting this analysis to ensure the proposed approach is appropriate. This will include assessing normality of the data using histograms and K-S tests. If the data does not meet these assumptions, we will run a non-parametric ANCOVA analysis. This will be determined once all data has been collected.

It is possible that the baseline and outcome variables may be skewed. Skew will be assessed using the traditional criteria based on their distribution (i.e., skews of greater or equal to 1.0

or less than or equal to -1.0). We will make a final decision about the best approach to address skew once this has been identified in the final data set. However, research suggests that the Tobit or two-part approach might be most appropriate (Boulton & Williford, 2018).

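### Section 6.9 prescribes a logistic first stage for a session count, yet names 2SLS and promises a first-stage F-test; these cannot all be carried out, and compliance is left undefined

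*SAP*

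**What the plan says.** SAP Section 6.9 commits to a CACE analysis, labelled exploratory, and names the estimator: "This will be estimated using two-stage least squares (2SLS) regression". It then sets out the steps.

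- First-stage response and predictors: "The first stage will model the compliance variable (i.e. number of sessions) using the same explanatory variables used for the primary analysis".
- First-stage model: "This will be a logistic regression model used to generate predicted compliance".
- Second stage: "The second stage models will use predicted compliance in place of the allocation group variable in the ITT primary analysis".
- Reporting: the first-stage results, "along with the correlation between the instrument and endogenous variable and the associated F-test".

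The explanatory variables of the primary model (Section 6.2) are baseline SRDS, area and allocation, where the allocation term "is a dummy variable for allocation group, i.e. 1 for the treatment group and 0 for the control group". Allocation is therefore a first-stage predictor.

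Section 4.1 describes what controls get: "Those randomly allocated to the control group receive light-touch, structured signposting and safeguarding support, provided by MAC". Section 6.9 does not say whether a control participant can count as a complier, gives no rule that turns sessions into a yes/no variable, and does not say how second-stage standard errors are obtained.

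**The concern.** The instructions cannot be followed as a set. An analyst would have to drop either the count or the logistic model, and would choose any cut-off after seeing attendance and outcome data. The cut-off decides which effect is estimated, so the analysis would not be pre-specified in the part that matters most.

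There is also a technical risk. 2SLS uses a linear first stage. Because allocation is randomised, it then remains consistent even if the outcome's relation to baseline is mis-specified. Fitted values from a logistic first stage are a non-linear function of baseline, so part of the estimate comes from curvature and not from randomisation. The ordinary standard errors of a second stage fitted by hand are also not the 2SLS standard errors.

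**Working it through.** **Base figure.** Section 6.9 contains no number, so the trial's own sample size was reproduced first (Section 5.1: MDES 0.20, pre-post correlation 0.5, two-sided 0.05, 80% power, 1:1). Per arm: 2 × (1.960 + 0.842)² × (1 − 0.5²) / 0.20² = 2 × 7.849 × 0.75 / 0.04 = 294.3, so 295 per arm and 590 in all, against the stated 592. The difference is negligible. Section 5.1 also gives 367 as the more realistic analysed number, and both sizes were used below.

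**1. Can the first stage be fitted?** A binary logistic fit to a session count stops with an error, because the response must lie between 0 and 1.

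**2. What if sessions are dichotomised?** Assume no control complies. Example at 296 per arm: control 296 non-compliers and 0 compliers; treatment 82 and 214. The allocation coefficient is 7.6 after 5 iterations, 12.6 after 10, 22.6 after 20 and 38.6 at a cap of 100. Its standard error goes from 0.9 to 3.9 million. The log-likelihood settles at −171.319 and the fitted control probabilities go to 0. This is quasi-complete separation: the fitted values are usable, but the allocation coefficient, its standard error and its Wald test are not. In separate normal-data runs at N = 367 the median Wald p for allocation was 0.999, although allocation is a very strong instrument.

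**3. How much does the missing definition matter?** With no control compliers, CACE = ITT effect / proportion complying in the treatment arm. For an assumed ITT effect of 0.20: 0.20/0.90 = 0.22; 0.20/0.70 = 0.29; 0.20/0.50 = 0.40.

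**4. How does the plug-in perform?** The SAP gives none of the inputs needed, so these are assumptions: a dichotomised compliance variable met by about 70% of the treatment arm, no control compliers unless stated, and ordinary second-stage standard errors unless stated.

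With constant-variance normal errors, a normal or skewed baseline, a linear or curved baseline relation and compliance depending on baseline and an unmeasured confounder (1,500 trials per scenario, N = 592 and 367, true effect 0, −0.2 or −0.5 SD), plug-in coverage was 94.3-96.1% and bias at most about 0.013 SD. Linear 2SLS coverage was 94.5-95.5%.

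Rejection under a true null at N = 367, from several sets of 600 to 1,200 trials per scenario:

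| Assumed data | Plug-in, ordinary SE | Plug-in, HC3 SE | Linear 2SLS |
|---|---|---|---|
| Normal, or skewed with constant variance | 4.0-5.7% | not run | near nominal |
| Skewed baseline, mildly non-linear mean | 5.3-5.9% (bias up to 0.03 SD) | not run | not tabulated |
| Variance rising with the mean, compliance dependent on baseline | 1.1-2.3% (negative slopes), 10.2% (slope +1) | 4.0-5.5% | not tabulated |
| Overdispersed counts, compliance dependent on baseline | 1.0-10.1% | 3.8-4.8% | 3.5-5.2% |
| Skewed SRDS-like scores, slopes −0.5, −1.0, −1.5, +1.0 | 1.6%, 2.1%, 2.2%, 17.1% | not run | 6.2%, 4.9%, 4.4%, 6.1% |
| Overdispersed count or log-normal scores | 1.4-17.4% (bias −0.08 to +0.07 SD) | not run | 3.8-5.8% (bias at most 0.007 SD) |

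Robust standard errors bring plug-in rejection back to nominal where they were tried, which points to unequal variance as the main cause.

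**The case against.** The best defence is that this is loose wording in an analysis the SAP calls exploratory. An analyst would pick a cut-off or a linear model and carry on, and the primary result would not change. That limits the importance of the point but does not remove the contradiction.

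Three stronger readings are tempting, and the document does not support them.

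- *The first stage separates completely and the analysis collapses.* The treatment arm would contain both compliers and non-compliers, so separation is only quasi-complete, and the second stage needs only the fitted values. That no control receives Cerridwen sessions is implied, not stated; Section 6.9 itself allows for the case "if some young people in either trial arm do not adhere to their assigned treatment". With 5% of controls counted as compliers there is no structural separation (N = 592, true effect −0.20: plug-in mean −0.200, coverage 94.9%).
- *The planned instrument check would point the wrong way.* The diagnostics the SAP names are a correlation and an F-test, not a logistic Wald p-value. The correlation would show a strong instrument. The Wald test would mislead only as part of the reported first-stage results.
- *The plug-in estimate is miscalibrated in general.* Skew alone did no damage. Distortion needed unequal variance together with baseline-dependent compliance, and it was conservative for the negative slopes. No slope comes from the SAP.

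It can also be said that Section 6.2 checks linearity and homoscedasticity first and mentions non-parametric, Tobit or two-part alternatives, so the linear second stage might not be used. That is fair, but Section 6.9 does not say what the CACE second stage would then become. Finally, this is not the only look at engagement: Section 6.5 plans a dosage analysis, although it is associational and conditional on power. Its mention of eight sessions is an example question, not a compliance definition.

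**Conclusion.** The point stands as an internal contradiction with an undefined compliance variable. A count response, a logistic model, 2SLS and a first-stage F cannot all be delivered, and this follows from the text alone. If compliance is dichotomised and no control can comply, the first-stage allocation coefficient, its standard error and its Wald test would be meaningless, while the fitted values would not.

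The effect on error rates is conditional: null rejection from about 1% up to 10-17% with overdispersed count-like scores and baseline-dependent compliance at N = 367, and close to 5% otherwise. The adverse case is plausible, because the SRDS volume score sums event counts and Section 6.2 anticipates skew, but it rests on assumed scenarios and on ordinary second-stage standard errors. The undefined threshold has the larger effect on what would be reported (0.22 to 0.40 from the same ITT effect). The analysis is exploratory and the primary ITT result is untouched, so this should be corrected but does not threaten the trial's main conclusion.

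**What to change.** In Section 6.9:

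1. Delete the logistic regression.
2. Choose one compliance variable now: the session count, which gives a per-session effect, or one stated binary definition, which gives a complier effect. These are different estimands, so both should not be left open.
3. State how control participants are coded.
4. Specify a linear first stage on allocation, baseline SRDS and area, fitted jointly with the second stage in a 2SLS routine, with allocation as the only excluded instrument, robust 2SLS standard errors and the F from the linear first stage.

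The cost is a few sentences of SAP text. No new data are needed for treated participants: Section 6.5 already has the delivery team recording their sessions. The change brings the section into line with the method it names.
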